continue to be followed by their primary care provider for the duration of the study. Nurses will assess for depressive symptoms at their initial session with participants using the PHQ-2. Participants will be informed of a positive screen and advised to contact their primary care provider or behavioral health professional. Primary care providers will also be informed of a positive screen. Nurses will be in communication with primary care providers for any concerns regarding the health status of study participants and all participants will be advised that communications with the nurse on the patient portal are for non-urgent medical concerns. Both patient portals specify that communication with providers is for non-urgent medical questions.

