3.3 Objectives

[figure not shown]
The primary objective of Phase 1 is to optimize components of the *MAP* intervention for adults with T2D who access healthcare at CHCs. To accomplish this aim, we will conduct interviews/focus groups with adults with T2D and health care providers (n=24) from two CHCs to inform details of intervention design and to identify perceived barriers and facilitators to the delivery of the intervention. We will use these qualitative findings to finalize the *MAP* protocol. The primary objective of Phase 2 is to determine the effect size of *MAP* on the primary outcomes of portal use (number of logins) and A1C, among adults with T2D (n=30) who access healthcare at two CHCs. Secondary outcomes include: a) patient engagement with care (clinic appointments, referrals, ER visits, hospitalizations, use of community resources for social determinants of health); b) T2D clinical management (EMR data of A1C, blood pressure, lipid profile, BMI); c) T2D self-management (medication, blood glucose monitoring, healthy eating, physical activity); d) psychosocial outcomes (diabetes self-efficacy, autonomy support, and diabetes distress); e) technology outcomes (digital literacy, acceptance/use/confidence); and f) satisfaction. Using a within subjects, pre-post design we will pilot *MAP* in 30 adults with T2D who are not currently using the patient portal. Data will be collected at baseline, 3, and 6 months. We will also rigorously evaluate the feasibility of *MAP* using an established framework (acceptability, demand, implementation, adaptation, and integration).

4 Study Design

We will use mixed-methods to develop and evaluate *MAP* for adults with T2D. This project will be conducted in two phases. In Phase 1 we will use a qualitative descriptive design, convening interviews/focus groups with stakeholders to guide the development of *MAP*. During this phase we will finalize the intervention protocol and develop promotional and training materials. In Phase 2 we will train personnel in intervention delivery (one community health worker [CHW] and one nurse at each CHC) and inform other health care providers at the clinics (e.g., physicians, pharmacists) about *MAP*. We will then implement *MAP* and evaluate the preliminary efficacy and feasibility of *MAP* using a pre-post design. IRB approval will be obtained prior to start-up of Phase 2.

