5.2 Number of Participants

For Phase 1, we will recruit health care providers (n=5), CHWs, (n=2), and adults with T2D (n=5), at each clinical site (total sample: 10 providers, 4 CHWs, and 10 adults with T2D).

For Phase 2, we will recruit 30 adults with T2D (n=15 from each clinic).

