If eligible and interested, a trained RA will enroll participants from the CHCs. The RA will obtain written informed consent and collect data (in English or Spanish depending on preference). We will use REDCap™, an NIH-supported, FDA-compliant electronic data capture application for data collection and storage. RAs will enter data at the time of data collection into the database via tablets. Trained RAs or nurses will obtain point-of-care A1C values with a fingerstick of blood, following all protocols for safety.

All participants who enroll in the study will receive standard T2D care at their CHC and the *MAP* intervention. The *MAP* intervention consists of 4 components:

1. Supplies/Needs: Provision of tablet, provision of an approximately 6-month data plan (until study completion), and referral for community resources such as food or housing assistance. Participants will keep the tablet after they finish the study. Tablets will be set to the appropriate language (English or Spanish per participants preference).

2. Technology Training: In-person training and ongoing support on how to use the patient portal with their tablet by trained community health workers (CHW) or nurse from the respective clinics. The CHW or nurse will give participants their tablet with data plan. They will meet 1:1 with participants in person or by telehealth. Sessions will cover: 1) how to use the tablet; 2) how to use the portal; 3) social determinants needs assessment; and 4) connection to community resources. The number, duration, and spacing of sessions will be determined by clinical need and participant availability, but it is anticipated that participants will have 4-6 individual sessions of approximately 30 minutes each over the course of the first month of the intervention. Sessions will be conducted face-to-face in the clinic or over secure telemedicine through MyChart/Healow. During the first or second session, the interventionist will conduct a screening for the social determinants of health (eg, housing, food, utilities). According to existing clinic protocol, participants with any such needs will be given referrals to community resources and assistance with accessing them such as completing an application for subsidized housing or obtaining groceries from a food bank.

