7.2 Planned Analyses

Phase 1 analysis:

The sample of participants in the interviews/focus groups will be described using frequency distributions and appropriate summary statistics (SAS version 9.4). Content analysis will be used to analyze qualitative data from each type of stakeholder along with field notes and interviewer observations (Hsieh, 2005) Rigor for this process includes: (a) transcribing taped interviews; (b) checking transcripts against tapes for accuracy; (c) developing coding categories by two members of the research team; (d) assigning codes of text with appropriate checks; (e) reviewing coded data to identify themes across participants; and (f) a team approach to data analysis. At research team meetings we will assess researcher bias, coding saturation, and interpretative congruence. Results will be used to finalize the intervention protocol for implementation in Phase 2

Phase 2 Analysis: Data will be collected in the form of questionnaires online on the secure REDCap system. A1C data, electronic medical record data and patient portal data will be entered into REDCap or Excel and merged into one database. All data that are downloaded from REDCap or Excel will be onto a Yale server, which has several secure firewall systems. Descriptive analyses will be performed to assess demographic and clinical characteristics of the sample. Feasibility data will be summarized. Distributions of outcome variables will be examined for central tendency and dispersion. We will estimate the Cohen's D effect size of MAP on A1C and will examine the intervention effect over 6 months using generalized linear mixed model (GLMM) with random intercept, which will incorporate the correlation within repeatedly measured A1C. The slope of time will represent the average change of A1C over 6 months. The GLMM will include all participants with data at baseline and at least one of post-intervention value and will handle missing data using maximum likelihood approach. To confirm findings with missing data, we will rerun the GLMM with multiple imputations which will be produced by assuming multivariate normal distribution of repeatedly measured A1C. Number of logins and the repeatedly measured secondary outcomes will be analyzed with the same approach using the GLMM. Residuals will be assessed for normality assumption and

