variables will be transformed with an appropriate form when the normality assumption does not hold. Count data such as portal use, clinic appointments, ER visits, and hospitalizations will be modeled using Poisson or Negative Binomial regression model. For exceeding zero count (i.e. a high proportion of no appointment, ER visit, hospitalization), zero-inflated regression models will be employed. We will also estimate the effects of portal use (frequency, type) and feasibility factors (e.g., acceptability, attendance, fidelity) on A1c at 6 months after controlling for baseline A1c using generalized linear model (GLM). For future research with a large sample size, we will obtain an effect size (partial eta square) of each factor from GLM. Qualitative data will be analyzed using the aforementioned content analysis approach.

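### The exploratory 6-month A1C models omit clinic, so a difference between the two clinics can be credited to portal use, attendance or fidelity

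*Combined protocol and SAP*

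**What the plan says.** Section 5.2 sets recruitment by clinic: "For Phase 2, we will recruit 30 adults with T2D (n=15 from each clinic". Section 4 provides for "one community health worker [CHW] and one nurse at each CHC". Portal data are extracted by each clinic's own staff (sections 6.6 and 8.5). Fidelity is assessed by the interventionists themselves, with review by the investigators (section 8.2).

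On the portal, section 2.2 states "Both patient portals specify that communication with providers is for non-urgent medical questions", and section 6.1 says sessions take place "face-to-face in the clinic or over secure telemedicine through MyChart/Healow". The text does not say which clinic uses which product. One product per clinic is the natural inference, but it is an inference.

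Section 7.2 describes every Phase 2 model:

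- The A1C model is a "generalized linear mixed model (GLMM) with random intercept, which will incorporate the correlation within repeatedly measured A1C", with the slope of time as the effect. The random intercept is for repeated measures within a person.
- Logins follow the same approach, with Poisson, negative binomial or zero-inflated versions for counts.
- A further model is announced: "We will also estimate the effects of portal use (frequency, type) and feasibility factors (e.g., acceptability, attendance, fidelity) on A1c at 6 months". Baseline A1C is its only named adjustment. It is to yield a partial eta square for each factor, for use in a larger study.

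None of these models names clinic, site, portal or interventionist. Sections 7.2.1 to 7.2.3 and 7.7 add no such term.

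**The concern.** Clinic coincides with the nurse, the CHW, the person who extracts the logins, the person who rates fidelity and, probably, the portal software. Login counts, attendance and fidelity scores may therefore differ between clinics for reasons unrelated to any individual's engagement. If 6-month A1C also differs between clinics after baseline adjustment (case mix, usual care, staff), a GLM without clinic cannot tell the two apart and reports the clinic gap as an effect of the factor.

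The quantity at risk is one the pilot is meant to hand on: the partial eta squares for planning the larger study. A lesser matter is that pooling logins over two clinics hides whether use rose at both or at only one, which is a basic feasibility question for a portal intervention.

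**Working it through.** **What the documents supply.** There are 15 people in each of two clinics (section 5.2), an A1C SD of 1.2 and a correlation of 0.57 over 6 months (section 7.1). They give no clinic contrast, no intraclass correlation and no login mean or SD, so every clinic input below is an assumption. The plan's one precision figure, ±0.27% for A1C change, follows from its SD of change: 0.72/√30 = 0.131, and 2.045 × 0.131 = 0.27. However, SD 1.2 and r 0.57 give an SD of change of 1.2 × √(2 × 0.43) = 1.11, not 0.72. That is a separate matter. Only 1.2 and 0.57 are used here.

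**The 6-month A1C model.** The factor has no effect within either clinic.

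- Residual SD of 6-month A1C given baseline: 1.2 × √(1 − 0.57²) = 0.99.
- Clinic gap in adjusted 6-month A1C: g = 0.3, 0.5 or 0.8%.
- Share of the factor's variance lying between clinics: s = 31%, 60% or 80%. The 31% corresponds to clinic login means of 10 and 30 with a within-clinic SD of 15: 10²/(15² + 10²) = 100/325.
- Clinic difference in the factor, in within-clinic SDs: d = 2√(s/(1 − s)) = 1.34, 2.45 or 4.00.
- Expected spurious slope without clinic: −(d·g/4)/(1 + d²/4). At s = 31% and g = 0.3 this is −0.1005/1.449 = −0.07. At s = 80% and g = 0.8 it is −0.8/5 = −0.16% A1C per within-clinic SD.

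Simulation with 4,000 trials per cell, two-sided 5%:

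| s | g (% A1C) | P(p<0.05), no clinic | Mean partial eta², no clinic | P(p<0.05), with clinic |
|---|---|---|---|---|
| 31% | 0.3 | 7% | 0.041 | 5% |
| 31% | 0.5 | 11% | 0.054 | 5% |
| 31% | 0.8 | 20% | 0.076 | 5% |
| 60% | 0.3 | 10% | 0.050 | 5% |
| 60% | 0.5 | 17% | 0.069 | 5% |
| 60% | 0.8 | 37% | 0.118 | 5% |
| 80% | 0.3 | 11% | 0.052 | 5% |
| 80% | 0.5 | 22% | 0.081 | 5% |
| 80% | 0.8 | 46% | 0.142 | 5% |

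With clinic in the model the mean slope is zero and mean partial eta² is about 0.037, its chance level at this sample size (1/27 with 26 residual degrees of freedom). With g = 0 the rejection rate is about 5% with or without clinic.

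The price of adjustment is a larger standard error for the factor, by roughly 1/√(1 − s): 1.2, 1.6 and 2.2 times at s = 31%, 60% and 80%.

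**Logins, for inference to these two clinics.** With assumed means of 10 and 30 and a within-clinic SD of 15:

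- Pooled SD: √(15² + 10²) = 18.0. Half-width: 2.045 × 18.0/√30 = 6.7.
- By clinic: 2.048 × 15/√30 = 5.6. The pooled interval is 6.7/5.6 = 1.20 times as wide.

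With negative binomial counts (mean 12 per 3 months, dispersion 0.5) and clinic ratios of 1.5, 2 and 3, the pooled SE is 1.80, 2.00 and 2.47, against 1.74, 1.84 and 2.11 by clinic. That is 3%, 9% and 17% too large. Coverage of the pooled interval is 94 to 96%.

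**Which term is needed for logins.** Section 5.3 requires no current portal use at entry, so clinic differences in logins arise after baseline. They are clinic-by-time differences. A clinic main effect alone, alongside a participant intercept, recovers at most part of the gain.

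**The case against.** The strongest reply is that this is a single-arm pilot with no specified hypotheses (section 3.2), that the GLM is exploratory, and that no decision hangs on a 5% test. That stands, and it limits the severity. It does not remove the point, because the partial eta squares are themselves inflated and are the intended product of that model.

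It can also be said that every figure above rests on assumed clinic differences. That is correct. At the low end (31% between clinics, 0.3% A1C) the error rate is only 7%, and if the clinics do not differ in A1C nothing is distorted.

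Several stronger readings are tempting, and the documents do not support them:

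- *The login interval is invalid.* For these two clinics it is somewhat too wide, hence conservative. Generalising to other clinics is a different problem. Two clinics cannot support an estimated between-clinic variance, and a fixed effect would not repair it.
- *The mean A1C change is biased.* A constant clinic difference in A1C level is absorbed by the participant intercept.
- *Fidelity is almost a clinic-level variable.* CHWs complete a checklist after each session, 4 to 6 individual sessions are anticipated, a CHW or a nurse may give the technology training, and the nurse delivers a second component (section 6.1). Variation between participants is therefore to be expected. Its share is unknown.
- *The plan states that each clinic has its own portal product.* It states that there are two portals and names two products. The pairing is inferred.

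**Conclusion.** The point holds for the 6-month A1C GLM. Clinic is tied to the factors under study and is left out, so any clinic difference in 6-month A1C is attributed to portal use, attendance or fidelity. Under assumed gaps of 0.3 to 0.8% A1C and between-clinic shares of 31 to 80%, the false-positive rate is about 7 to 46%, and mean partial eta² rises from about 0.037 to between 0.04 and 0.14. With clinic included, the error rate is about 5% and the bias disappears. The actual size cannot be set from the documents.

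For logins the point is mainly one of reporting. Pooling conceals differences between clinics, and the precision gained by separating them is modest, about 3 to 20% under the assumed differences.

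For a 30-person pilot this is a moderate gap that is cheap to close before the data are analysed.

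**What to change.** In section 7.2:

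1. Include clinic as a fixed covariate in every GLM of 6-month A1C. State that a factor varying almost only between clinics cannot be separated from clinic (nor portal from nurse or CHW), and that its effect will then be reported as not estimable rather than as a partial eta square.
2. Report 3- and 6-month logins by clinic, naming the portal at each. If clinic enters the login model, use clinic-by-time rather than a main effect alone, and give the overall estimate as the equally weighted average of the two clinics.
3. Say which clinic uses which portal.

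The cost is SAP wording, 1 to 2 degrees of freedom and less precise factor estimates, which reflect what 15 people per clinic can show. No new data or additional login outcome are needed, since Table 1 already lists features used, messages and glucose uploads alongside logins.

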In Phase 2, we will use a pre-post design, collecting data from participants at baseline, 3 and 6 months. We will evaluate change over time in participants.

Study Design:

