Attendance will be recorded and CHWs will complete a fidelity checklist after each session. The CHWs will remind participants about sessions. Once technology competence has been established through a teach-back method, participants will be connected with the nurse at each site. Interventionists will remain available after these sessions are concluded, in case participants have additional needs/questions regarding material needs and/or tablet/portal use. Participants will be given the contact information for the interventionist and encouraged to contact them with any questions.
See Appendix X for details of this component of the intervention.
3. Diabetes Support: Diabetes self-management support will be provided by a nurse via the patient portal. The nurse will have an initial in person or telehealth session with participants to assess their diabetes self-management challenges and successes. Nurses will assess for depressive symptoms at their initial session with participants using the PHQ-2 (an established depressive symptom screener for primary care). Participants will be informed of a positive screen and advised to contact their primary care provider or behavioral health professional. Primary care providers will also be informed of a positive screen. At this meeting the nurse and participant will co-create a diabetes self-management plan aligned with their treatment plan prescribed by the participants' primary care provider. The nurse will work with each patient to individualize diabetes behavioral targets, considering the following priorities: use of the portal, attendance at appointments, uploading of blood glucose data to the portal, medication refills and adherence, and lifestyle and emotional factors. After this initial session, the nurse will proactively contact participants via the portal approximately 2 times/week or as clinically indicated for 3 months to check-in, provide diabetes education, provide motivational support, and/or answer any participant questions about their diabetes. After 3 months, the nurse will check-in with participants one time per week. See Appendix X for details of the intervention.
4. Text Messages: CHWs and nurses may also send text message reminders to participants for appointments or to check/use patient portal.

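### A1C change over 6 months is summarised by one linear slope, which with complete data takes nothing from the 3-month mean, so the planned estimate cannot show the time course of an intervention whose intensity changes by design

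*Combined protocol and SAP*

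**What the plan says.** Section 4 (Study Design) sets the Phase 2 visits and the intent: "collecting data from participants at baseline, 3 and 6 months. We will evaluate change over time in participants".

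Section 7.2 examines the A1C effect with a "generalized linear mixed model (GLMM) with random intercept, which will incorporate the correlation within repeatedly measured A1C", and adds: "The slope of time will represent the average change of A1C over 6 months". A single slope means that time enters as one linear term. On who is analysed: "The GLMM will include all participants with data at baseline and at least one of post-intervention value". Sections 7.2 and 7.7 add a rerun with multiple imputation from a multivariate normal distribution for repeated A1C.

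Two other A1C analyses appear in 7.2. One is a standardised effect, "We will estimate the Cohen's D effect size of MAP on A1C", with no time point given. The other is a regression of 6-month A1C on portal use and feasibility factors, adjusted for baseline, which does not estimate change over time. Neither 7.2 nor 7.7 plans a categorical visit term, a curvature term or a visit-specific contrast for A1C.

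Section 6.1 describes an intervention that is not constant over time. Technology training is anticipated as "4-6 individual sessions of approximately 30 minutes each over the course of the first month of the intervention". The nurse then holds an initial session and makes contact through the portal about twice a week for 3 months. Later contact is lighter: "After 3 months, the nurse will check-in with participants one time per week".

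**The concern.** The plan collects A1C at three visits and intends to evaluate change over time, but its A1C summary assumes a constant rate of change. The contact schedule does not support that assumption. With equally spaced visits, the middle visit also drops out of the slope.

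What is at stake is what the pilot can tell the larger study for which Section 7.1 says it provides preliminary data: whether A1C moved early, steadily or late, and whether an early change was kept. A second, smaller matter is that participants with only a 3-month follow-up enter the model. When 6-month values are missing, the line extrapolates from 3-month data.

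**Working it through.** **Inputs.** Visits at 0, 3 and 6 months (Section 4). Random intercept, so equal correlation between visits, and a linear time term (7.2). n = 30, SD 1.2, correlation 0.57, stated SD of change 0.72 (7.1). The sizes of fall and the missing-data rates are assumptions chosen for illustration.

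**The plan's precision figure.** 0.72/√30 = 0.131, and 2.045 × 0.131 = 0.27, which matches the stated margin. The stated SD and correlation give a different SD of change: 1.2 × √(2 × 0.43) = 1.113. Then SE = 1.113/√30 = 0.203 and half-width = 2.045 × 0.203 = 0.42. That mismatch is a separate matter, so both half-widths are used here as a range.

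**Complete data.** The time deviations from their mean are -3, 0 and +3, with sum of squares 18. The slope is (3·y6 - 3·y0)/18 = (y6 - y0)/6. Six times the slope therefore weights the visits -1, 0, +1.

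| Change at 3, 6 months | Estimated 6-month change |
|---|---|
| -0.8, 0 (full fade) | 0.00 |
| -0.8, -0.4 (half fade) | -0.40 |
| -0.8, -0.8 (early) | -0.80 |
| -0.4, -0.8 (steady) | -0.80 |
| 0, -0.8 (late) | -0.80 |

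The 3-month value still enters the residual variance. If actual dates are used and the middle visit falls at month 3.5 for everyone, its weight is 0.11.

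**6-month values missing.** Generalised least squares with SD 1.2 and correlation 0.57:

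| Missing at 6 months | 3-month weight | 6-month weight | 0.5 fall fully lost (truth 0) | 0.5 fall only after month 3 (truth -0.50) |
|---|---|---|---|---|
| 10% | 0.049 | 0.975 | -0.025 | -0.488 |
| 20% | 0.107 | 0.946 | -0.054 | -0.473 |
| 30% | 0.177 | 0.911 | -0.089 | -0.456 |

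The fourth column is the 3-month weight × -0.5. The last is the 6-month weight × -0.5.

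**Planned multiple imputation.** A multivariate normal imputation need not force the means onto a line. Once month 6 is filled in, the weights return to -1, 0, +1. In simulation with month 6 missing completely at random, the imputed slope averaged -0.01 for the full fade and -0.50 for the late fall, at both 20% and 30% missing.

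**Categorical visit instead.** With complete data the 6-month contrast is y6 - y0 with SE 0.203, identical to six times the slope. The 0-to-3 and 3-to-6-month contrasts also have SE 0.203. With missing 6-month values the SE of the 6-month contrast is 0.220 against 0.219 for the slope at 20%, and 0.231 against 0.229 at 30%.

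**Chance of detection.** For a 0.5 fall at 3 months fully gone by 6 (4,000 simulated trials of 30, complete data), with SD of change 1.11 the slope test rejects in 4%, a 2-df visit test in 69% and a paired 3-month contrast in 66%. With SD of change 0.72 the figures are 2%, 97% and 95%. The slope's rates are not lost power for a 6-month effect, since none exists in this scenario. They show that the slope does not respond to the 3-month change.

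**The case against.** The strongest reply is that the primary estimate is sound. With complete data the slope gives the 6-month change exactly, and the proposed primary contrast gives the same number with the same SE. That stands. A reader might infer that the planned A1C effect is wrong, but as a 6-month change it is not.

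A reader might also infer that missing 6-month data would seriously bias the result. The documents do not support that. The bias is under 0.1 in these scenarios, well inside the confidence interval, and the imputation rerun already in 7.2 and 7.7 largely removes it, although that rerun is confirmatory rather than primary.

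It is too strong to say that the trial could never see a 3-month effect. The 3-month values are kept, outcome distributions will be examined, and a Cohen's d is planned. However, none of these is tied to a visit or carries a commitment to a 3-month estimate with an interval.

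Nor do the documents predict that an effect will fade. Section 3.2 specifies no hypotheses, weekly nurse contact continues, and the full fade is an extreme case.

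Finally, month 3 does not mark the step-down. The 3 months of twice-weekly contact run from the initial nurse session, which follows training, so step-down may fall nearer month 4. A 3-to-6-month contrast spans it without isolating it.

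**Conclusion.** The point holds in a limited form. The slope is a valid summary of 6-month change, but with complete data at nominal visits the 3-month mean has no influence on it. The planned effect estimate therefore cannot separate early, steady and late responses, or show an effect present at 3 months and gone by 6. After a partial fade it shows only what remains at 6 months. Linearity has no support in a schedule that is heavier early and lighter later.

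The missing-data bias is secondary: about -0.05 at 20% and -0.09 at 30% missing for a 0.5-point fall fully lost, against a half-width of 0.27 to 0.42. These figures rest on equal correlation between visits, SD 1.2, correlation 0.57 and the assumed trajectories. The change is worth making because it recovers time-course information from data already collected, at almost no cost. It does not correct an invalid primary result.

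**What to change.** In Section 7.2, enter visit (baseline, 3 months, 6 months) as a categorical factor in the A1C mixed model in place of the linear time term. Keep baseline-to-6-month change as the primary estimate. Report the baseline-to-3-month and 3-to-6-month contrasts with 95% CIs, and note that the latter spans the step-down in nurse contact without isolating it. Run the multiple-imputation analysis with the same visit term.

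The cost is a short text change and one extra mean parameter. No visit, procedure or participant is added. With complete data the 6-month estimate and its SE are unchanged, and with up to 30% of 6-month values missing the SE rises by about 1% or less.
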